2.3.3. Study Phase I

Phase I is the observational phase of the study, during which a thorough assessment of each participant will be performed.

H2020 Contract No 818110

2.3.3.1. Measurements

Measurements concern sociodemographic information, dietary and other lifestyle behaviors, anthropometry, medical history, genotype, metabolomics profile (in blood and urine), and microbiome.

o Sociodemographic information

Sociodemographic information will be collected from all children [21, 22]. In specific, the age (in years), the number of people living with (in the family and in the household), whether they attend school (yes/no), and whether the school is private (yes/no) will be recorded. Furthermore, information will be collected regarding parents' marital status (1; married, 2; unmarried/co-habiting, 3; single parent, 4; divorced or separated, 5; widowed), parent's origin (1; White, non-Hispanic; 2; Black, non-Hispanic; 3, Hispanic; 4, Asian; 5, other), years of education described by the number of educational years (mother and father separately), the maternal and the paternal occupation [1, unemployed; 2, employee in private sector; employee in public sector; 3, self-employed; 4, working without pay in family business; 5, on leave (excluding maternity); 6, pensioner]. Finally, the mother or the father will be asked to self-characterise their annual family and household income (ranging from 1, 0-4,999 € to 9, over 50,000 €) and whether the child has active health insurance (yes/no).

Dietary assessment

Three methods of dietary assessment will be employed during Phase I, namely a 4-day food record supported by a mobile app (for food pictures uploading), an extensive semi-quantitative food frequency questionnaire (FFQ) and a short questionnaire assessing diet quality (KIDMED). We aim to cross-match intake data, and compare the validity of the FFQ against the 4-day food record. The dietary assessment modality that proves to be the most valid will be used in phase II and, finally, in the platform. The mobile app will be developed in the context of WP6, and will serve as an adjunct to the 4-day food record, so as to examine its additive value in improving dietary assessment of children. Finally, the KIDMED will be used as a quick index of dietary quality, which can be easily incorporated in the platform. All the dietary assessment means will be thoroughly described below.

Regarding the 4-day food record, all children with the help of their caregivers (for ages <9 years) will be asked to record all foods and drinks consumed for three consecutive weekdays and one day of the weekend and bring it to the hospital the day that Phase's I assessments are to be performed. Nutrients

H2020 Contract No 818110

intake will be calculated using a standard food analysis program [the Nutritionist Pro™ Diet Analysis software (Axxya Systems, Woodinville, WA, USA)]. The research team involved in the diet analysis is competent in using the proposed software, and HUA has a long history of analyzing dietary data through it. Another strength of the proposed software is that it comprises food databases from multiple countries, which can be used to extrapolate the most relevant and reliable reference. In order to extend and optimize the quantitative and qualitative information received from the food records, children will be asked to upload pictures of mixed foods and drinks to NUTRISHIELD application.

The second method of dietary assessment is the implementation of a semi-quantitative FFQ. This comprises 69 questions on the consumption of foods that are commonly eaten by various populations throughout a year, including dairy products, cereals, fruits, vegetables, meat, fish, legumes, added fats, alcoholic beverages, stimulants and sweets[23]. Using a 6-grade scale ("never/rarely", "1-3 times/month", "1-2 times/week", "3-6 times/week", "1 times/day", "≥2 times/day"), participants will be required to indicate the absolute frequency of consuming a certain amount of food, expressed in g, milliliters or in other common measures, such as slice, tablespoon or cup, depending on the food. The previous month will be set as the timeframe. The FFQ will be completed by the children with the help of the caregiver when needed.

Diet quality will be assessed by the KIDMED. The KIDMED was originally developed in an attempt to combine the Mediterranean diet characteristics as well as the general dietary guidelines for children in a single index [24]. It was based on the principles sustaining healthy, Mediterranean dietary patterns (e.g. daily fruit and vegetable consumption, weekly fish and legumes intake), as well as on those that undermine it (e.g. frequent fast-food intake, increased consumption of sweets). The index comprises 16 questions in the form of "yes or no": questions denoting a negative connotation are assigned a value of -1 and those with a positive aspect +1. Total score ranges from -4 to12 and it is divided into three levels: (1) \geq 8, optimal Mediterranean diet; (2) 4-7, improvement needed to adjust intake to Mediterranean diet; (3) \leq 3, very low diet quality. It has been used so far in variety of settings and countries [25-27].

Other lifestyle behaviors assessment

Physical activity level of children will be evaluated using the self-administered 15-item Youth Activity Profile (YAP) [28]. Participants will be asked to report time spent on activities at school, leisure time activities outside of school, and sedentary behaviors. Participants will also report mean nocturnal sleep

duration (in hours/day) and whether they have a TV set in their room (yes/no). All questions regarding sedentary and physical activity behavior refer to the last week, except for sleep, which refers to the last month.

Smoking habits of the family will also be recorded [29]. The mothers of the children will be asked whether they smoked during pregnancy (yes/no) and whether they were exposed to smoke while pregnant more than 30 minutes/day (yes/no). What is more, children will be asked about themselves smoking: current smoking status (yes/no), smoking frequency (1, daily; 2, less than daily; 3, not at all), past smoking (yes/no), age of daily smoking initiation and date of smoking cessation.

Finally, intake of dietary supplements (e.g. vitamins) will be recorded and all children will be also asked whether they are medically diagnosed with dietary allergies or other diseases [1, lactose intolerance; 2, celiac disease; 3, medical diseases under restrictive dietary schemes (sub-question-please refer); 4, other (please refer)] and whether they follow a vegetarian (all sub-types) or vegan diet (yes/no). If the answer to the former question is positive they will be asked for further details [1, vegan; 2, lacto-vegetarian; 3, ovo-vegetarian; 4, lacto-ovo vegetarian; 5, other (please refer)].

Anthropometric assessment

Children's weight will be measured on leveled platform scale to the nearest 0.5 kg and height on a wall-mounted stadiometer to the nearest 0.5 cm. Body Mass Index (BMI) (kg/m²) will be calculated by dividing the weight in kilograms by the height in meters squared.

Medical history assessment

Children's medical history will be recorded by asking all the chronic conditions that they may have.

Genotype characterisation

A buccal swap sample will be collected from all children. In specific, standard buccal swab kits will be used to gather DNA sample for sample, as described in Deliverable 3.1.

Metabolome characterisation

For the characterisation of the children's metabolic profile, urine and blood samples will be collected as described in Deliverables 2.2 and 3.1.

Microbiome assessment

Fecal samples from all children will be collected for microbiome analyses. The protocol is described in Deliverable 2.1.

2.3.4. Study Phase II

2.3.4.1. Description of the Intervention

Personalized diet (Group A)

This intervention includes a personalized dietary plan derived from NUTRISHIELD platform. This plan will be based on the personalized nutrition algorithm taking into account genome analysis, dietary assessment, biochemical markers, socioeconomic status as well as any input having possibly emerged from the machine learning analyses from the evaluations performed during Study Phase I. In specific, in the beginning of the intervention period, taking into account the results from the evaluations performed in the observational period, a 4-week personalized dietary plan, derived as described above will be given to the children. Then, every month, for the following six months, visits will be arranged in the hospital with a window of ± one week, in order to perform the evaluations described below and the children to receive the new 4-week algorithm-derived dietary plans based on the previous month's evaluation. The intervention will be based on dietary guidelines presented in Table 1 [30], modified accordingly to address personal dietary, genetic and other needs, if important input emerges from Phase I.

Usual care diet (Group B)

The control dietary plan will be based on the same principles as the intervention diet [30], but without the use of the NUTRISHIELD platform and the personalized algorithm. Standard information and advice will be given instead by trained dieticians in face to face meetings. This phase will last six months and visits will be arranged once per month.

Table 2.1: Evidence-based guidelines on which intervention and usual care dietary plans will be based upon[30]

Guidelin	es
0	caloric restriction of 10% below energy needs
0	fat intake of 25-35% of total energy intake
0	saturated fatty acids <10% total energy intake
0	monounsaturated fatty acids >10% total energy intake
0	adequate mixture of n-6 and n-3 polyunsaturated fatty acids (PUFA, approximately 10 $\%$ of total energy
	intake)
0	fruit intake:
	o 1.5 cups per day for children 8-13 years old
	o 1.5 cups per day for girls aged 14-18 years
	o 2 cups for boys aged 14-18 years old
0	vegetables intake:
	o 1 cup per day for girls aged 8 years old
	o 1.5 cups per day for boys aged 8 years old
	o 2 cups per day for girls aged 9-13 years old
	o 2.5 cups for boys aged 9-13 years old
	o 2.5 cups per day for girls aged 14-18 years old
	o 3 cups per day for boys aged 14-18 years old
0	whole-grain breads and cereals intake:
	 4 oz per day for girls aged 8 years old
	o 5 oz per day for boys aged 8 years old
	o 5 oz per day for girls aged 9-13 years old
	o 6 oz for boys aged 9-13 years old
	o 6 oz per day for girls aged 14-18 years old
	o 7 oz per day for boys aged 14-18 years old
0	lean meat and legumes consumption:
	o 3 oz per day for girls aged 8-13 years old
	o 4 oz per day for boys aged 8-13 years old
	o 5 oz per day for girls aged 14-18 years old
	o 6 oz per day for boys aged 14-18 years old
0	low fat and non-fat dairy intake:
	o 2 cups per day for children aged 8 years old
	o 3 cups per day for those aged 9-18 years old
0	reduction of salt intake, including salt from processed foods
0	reduction of intake of sugar-sweetened beverages and foods
0	at least 20minutes of moderate to vigorous physical activity daily, with a goal of 60 minutes per week

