2.1. Background

Childhood obesity rates appear to have reached a plateau in western societies [1], yet the estimates remain alarmingly high. In the year 2016, some 124 million school-aged children worldwide were reported to be obese [1], a number possibly underestimated [2]. Excess body weight in childhood is associated with adverse health outcomes across the life span [3]. In light of the severe long-term effects of pediatric obesity [4], the disease calls for timely detection and therapy.

Having obesity is associated with metabolic abnormalities that predispose children to increased cardiometabolic risk [5]. This risk remains persistent during adulthood and is associated with an increased mortality risk [3]. Furthermore, obesity appears to consolidate during childhood and adolescence. Consequently, the obese child is highly likely to remain obese in adulthood [6].

Medical research has fairly recently suggested that children with obesity suffer from non-communicable diseases reportedly uncommon in childhood, that is type 2 Diabetes Mellitus (T2DM) [7, 8]. Other risk factors for the development of pediatric T2DM include familial history of the disease, being born to a mother with gestational diabetes and various metabolic abnormalities [9]. Unlike type 1 diabetes, T2DM is diagnosed at later stages and is associated with poor metabolic control [10], findings that could explain why youth with T2DM are in greater risk for developing earlier and more severe cardiovascular complications than children with type 1 diabetes [9].

Having diabetes, with or without concurrent obesity, calls for integrative lifestyle modification measures, with dietary management as cornerstone. Available guidelines for both youth obesity and diabetes agree on (i) the adherence to a healthful and culturally appropriate dietary pattern, (ii) the adoption of an active lifestyle, (iii) the promotion of adequate growth, and, when appropriate, (iv) weight reduction (up to 10% of initial weight) [11-13]. These modalities have been proven effective in the short term; lifestyle interventions in obese children have resulted in moderate weight reduction and ameliorated glycemic and cardiovascular indices [14-17]. Similar results have been produced for children

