2.3.1. Study design

The details of the study design where optimized following discussions with the NUTRISHIELD partners (during the meeting held on Athens 9-10/4/2019, mails exchange and teleconferences) to better serve the project purposes. Small deviations from the Description of Action were decided regarding the study design related to the groups and the timeline without altering the overall goals of the study.

The proposed study is a two-arm, parallel, randomized controlled study, with a dietary intervention for children (8-18 year old) with obesity or diabetes (type I or II). It will be carried out in Ospedale San Raffaele hospital between M19 to M41. The study protocol will be approved by the Ethics Committee, and written informed consent will be obtained from all caregivers and/or participants. All procedures regarding volunteers' recruitment and participation, data security and handling will be in absolute accordance with the principles set under Work Package (WP) 9, concerning Ethical Requirements, and more specifically stated on Tasks 7.1 and 7.2 and D 7.2.

H2020 Contract No 818110

The study will be divided into two phases:

- 1. **Phase I**: the **Observational** phase, lasting at least four months. During this period children will be recruited and their diet and biomarkers will be assessed once, as described below. At the end of the observational phase and recruitment period, the study will pause for nine months (from M23 to M31) in order to perform machine learning analyses, feed the platform and train the personalized nutritional algorithm with the results from the preceding assessments of the observational phase.
- 2. **Phase II**: the **Intervention** phase, lasting six months. During this period children recruited in the study will be randomly allocated to one of the two groups:
 - Group A (Intervention) will receive a NUTRISHIELD-derived personalized diet
 - **Group B (Control)** will follow the standard European dietary guidelines for obesity/diabetes, i.e. the usual care/control diet.

Diet as well as biomarkers and clinical data will be evaluated at the beginning and at the end of the intervention phase.

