2.3.2. Participants

Participants will be recruited at the San Raffaele Hospital (OSR). All visits and blood and urine sample collection will be held at the hospital. Fecal sample collection (for microbiome analysis) will be performed at home.

Inclusion criteria

Children with obesity and/or diabetes, aged 8-18 years visiting hospital on an outpatient basis.

Exclusion criteria:

- Children with any acute or chronic disease (tumor, infection, others), gastrointestinal diseases, cardiovascular disease, chronic renal disease, diseases of the parathyroid, diseases necessitating regular phlebotomies, and other chronic diseases which could affect the results of the study
- Use of medicine which could affect the results of the study, such as systemic glucocorticoids,
 lipid-lowering or anti-hypertensive drugs
- Recent weight loss or weight gain (> 3 kg), within the previous 3 months of the beginning of the study
- o Transfusion of blood in the last three months before Study Phase I
- Use of dietary supplements, including multivitamins, fish oil capsules, minerals, and trace elements (three months before and during the entire study period)
- Inability (physically or psychologically) to comply with the procedures required by the protocol.

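### Table 2.1 sets a 10% caloric restriction for both arms with no condition on weight status, although children with diabetes and no obesity are eligible

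*Protocol*

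**What the plan says.** **Who can enter.** Protocol section 2.3.1 describes a trial in children "with obesity or diabetes (type I or II"), and the inclusion criterion in section 2.3.2 is "Children with obesity and/or diabetes, aged 8-18 years visiting hospital on an outpatient basis". None of the exclusion criteria sets a lower limit on weight or BMI.

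**What they are prescribed.** Table 2.1 in section 2.3.4.1 is captioned "Evidence-based guidelines on which intervention and usual care dietary plans will be based upon", so it covers both arms. Its first line is "caloric restriction of 10% below energy needs". This is the only line that sets total energy. The food-group lines, by contrast, vary by age and mostly by sex, for example "1 cup per day for girls aged 8 years old" for vegetables.

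**Group B.** Section 2.3.4.1 states "The control dietary plan will be based on the same principles as the intervention diet", delivered as standard advice by dieticians at monthly visits. Section 2.3.1 says that this group "will follow the standard European dietary guidelines for obesity/diabetes, i.e. the usual care/control diet".

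**Group A.** The first plan takes account of the Phase I evaluations, and each later plan rests on the evaluation of the month before. The table may be modified for personal needs if Phase I yields important input.

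**The rationale.** Section 2.1 recognises diabetes both with and without obesity. It reports that guidelines for the two conditions agree on, among other aims, "iii) the promotion of adequate growth, and, when appropriate, (iv) weight reduction (up to 10% of initial weight").

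**The concern.** The eligibility criteria deliberately include children with diabetes who may carry no excess weight. The dietary table then sets energy below need for everyone. The authors conditioned the food-group amounts on the child's characteristics, but not the one line that creates a deficit.

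At stake is the care of growing children aged 8 to 18. Where the line is applied literally, a lean child with diabetes is given a plan below energy needs for up to six months. The protocol's own account of the guidelines offers no reason for doing so. The safeguard would then depend on a dietician or an algorithm departing from the written table.

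**Working it through.** This is a matter of reading sections against each other. The protocol gives no figure for it that could be reproduced.

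**Step 1: is a lean child eligible?** Sections 2.3.1 and 2.3.2 join obesity and diabetes with *or* and *and/or*, and no exclusion refers to low or normal weight. Yes.

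**Step 2: does the restriction reach that child?** The caption of Table 2.1 names both plans, and the energy line carries no qualifier. As written, yes, in either arm.

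**Step 3: does another stated rule exempt the child?**

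| | Group A | Group B |
|---|---|---|
| Basis of plan | Table 2.1, personalised by the algorithm | Same principles as Group A, without platform or algorithm |
| Weight, height, BMI available? | Yes: measured in Phase I (section 2.3.3.1) and among the Phase II measurements (section 2.3.4.2), which feed the plans | Yes: measured in all children |
| Stated clause for individual modification | Yes, conditional on Phase I input | None |
| Rule that lifts the restriction in a lean child | None | None |

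So in Group A the input exists and the rule is missing. In Group B there is neither a rule nor a stated route to one.

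**Step 4: does the line follow from the rationale?** Section 2.1 makes weight reduction conditional and lists adequate growth as an aim for both conditions. Table 2.1 does not carry the condition over.

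**Step 5: scale, as illustration only.** The protocol gives neither the share of lean children nor their energy needs. Both are assumed here.

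- Children concerned = 80 (Phase II total, section 2.3.5.1) × assumed share. For 10 / 20 / 30 / 40%: 80 × 0.10 = 8, 80 × 0.20 = 16, 80 × 0.30 = 24, 80 × 0.40 = 32, across both arms.
- Daily deficit = 0.10 × assumed need. For 1,600 / 2,200 / 2,800 kcal: 160 / 220 / 280 kcal per day.

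The point does not depend on these figures. It applies to any eligible child without excess weight.

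**The case against.** The strongest reply has four parts.

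1. **Group A's plans can respond to weight.** This stands. A reader might infer, because weight is not named in the list of algorithm inputs, that weight status cannot enter these plans. The documents do not support that: the plans rest on the Phase I and the previous month's evaluations, and anthropometry is among the measurements. What is missing is an energy rule.
2. **Section 2.1 is background.** This also stands. It summarises outside guidelines and prescribes nothing for this study, so there is no contradiction between two operative instructions. The mismatch is between the stated rationale and the table meant to carry it out.
3. **The table is a basis for plans, and trained dieticians apply it.** They may well not restrict a lean child. That reduces the likelihood of harm. It does not repair a line which, as written, tells them to restrict.
4. **The document calls itself a preliminary design and a model.** Individual energy prescription is indeed clinical detail. But the protocol chose to fix an energy target here, and fixed it without the condition that its rationale implies.

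A reader might also infer, from the two descriptions of Group B's diet, that lean children would receive different energy targets in the two arms. That would need knowledge of what the European guidelines say about lean children, and the documents do not reproduce them. Nor can the title of the table's source show whether that source conditions the restriction. Section 2.3.4.1 puts both arms on the same table, so a between-arm difference is not shown.

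**Conclusion.** The point holds in limited form. Table 2.1 fixes an energy restriction without a condition on weight status, for a population that includes children with diabetes and no obesity. This does not fit the growth aim and the conditional weight reduction in section 2.1. It holds most strongly for Group B. In Group A the restriction could be lifted, but nothing says that it must be.

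The size is unknown, because the protocol does not give the share of lean children. Nothing here shows an effect on power or bias in the comparison of the arms. The case rests on the table being followed as written and on at least one lean child with diabetes being enrolled. It deserves correction before Phase II because it concerns the safety of children and the correction is small.

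**What to change.** 1. **Table 2.1, both arms:** apply the 10% restriction only to children with excess weight for whom weight reduction is appropriate. For all others, prescribe energy that meets needs for growth. The investigators set the threshold, using the BMI already measured and the WHO growth charts already cited in section 2.3.4.3.
2. **Section 2.3.1:** align the description of Group B's diet with the amended Table 2.1, so that one statement governs its energy target.

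**Cost:** a condition in the table, a sentence in section 2.3.1, and a decision on the threshold. No new data are needed, and sample size, randomisation and analysis stay as they are. The downside is that less weight change is to be expected among lean children, but by the same rule in both arms.
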